3.2.2 Secondary

Budget impact analysis: Measures and analyses will follow best practice guidelines (Mauskopf et al., 2007). Dental public and private insurance claims will be collected from each participating site. Labor Costs: Labor time will be assessed for each dissemination scenario at each site and average salary for each personnel will be used to determine labor cost. We will measure costs of interface development, implementation, and technical support.

Pediatric oral health behaviors:

Brushing. We will assess frequency, duration, timing, and supervision of brushing using items from the BRFQ (Albino et al., 2017). This measure will be assessed at all measurement points, and during the TM program.

Bottle/sippy cup/cup use. This measure will be assessed at all measurement points, and during the TM program. We will use items from the BRFQ (Albino et al., 2017).

Diet (Food and Beverage Consumption Scale; Palmer et al., 2010; 31 food/beverage items). Participants are asked to assess their child's food intake by selecting the frequency in which each food item is consumed over the past month on a five-point Likert scale, which is scored from 0-4 and measured by the following choices: Never/Rarely; 1-2 times/week; 3-6 times/week; 1 time/day; 2 or more times/day. The food items presented are divided into 6 food categories: cereal; fruits and vegetables; grains, breads, and pastas; dairy; snacks and sweets; and drinks. Each food category contains approximately 2 or more foods or beverages. The estimated cariogenicity score is composed of 5 cariogenic categories, calculated for each child by obtaining a weighted sum of the number of food items for each food category and dividing by the total food and beverage items. This measure will be assessed at baseline, 4, 12, and 24 months after baseline.

Sugar sweetened beverage consumption (15 items). We will use the BEVQ-15 to assess sugar-sweetened beverages and total beverage energy intake (Hedrick et al., 2012). These measure will be assessed at baseline, 4, 12, and 24 months after baseline.

Tooth monitoring. We will assess the frequency of parental checking of child's teeth for early signs of cavities. This will be assessed at all measurement points. We will use items from the BRFQ (Albino et al., 2017). This measure will be assessed at baseline, 4, 12, and 24 months after baseline.

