5.4.2 Masking Procedures

All study staff collecting data, including the clinical examiners and RAs, will be blind to treatment condition. The Project Director and PIs will not be blind to treatment condition, because they will need to monitor inbound text messages for any responses that the automated system does not recognize. Unmasking procedures are detailed in the MOP.

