6.3 Procedures for Training Interventionists and Monitoring Intervention Fidelity

The intervention will not utilize human providers. TM interventions are delivered exactly as designed, resulting in a 100% reliable intervention, providing confidence in the obtained results. However, because the project director will be able to respond to TMs, we will review a proportion of the responses to ensure that there is no treatment contamination. Because our

outcome data is collected by a clinical examiner, this data collection will be digitally recorded by an RA to ensure that no oral health advice or education is given during that time.

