
Clinical Examiners will:

- Be equipped with medical emergency kits containing first aid supplies, epi pens, glucose gel, etc.

- Be Certified in Cardiopulmonary Resuscitation
- Be aware of emergency protocols at each pediatric clinic including emergency exits and location of telephones

Intervention Dose and Engagement:

Agile Health will send regularly scheduled reports which will include data regarding:

- Number of texts sent
- Percent of texts responded to
- Number prompted responses
- Use of program features
- Topics chosen
- Goals set/completed
- Ratings of TMs and program satisfaction

Budget Impact Evaluation:

We will survey IT specialists at all our sites as well as technical experts in industry to estimate interface and application costs of two different integration strategies involving the incorporation of the OHT intervention into routine clinical care: 1) a fully-automated strategy that involves an EHR prompt to providers recommending that they 'prescribe' the program to their patients and the system automatically enrolls the patient via an EHR to iSMILE and where a summary is returned to the EHR for guidance at future appointments; 2) a more labor intensive strategy but less technologically complex approach whereby the provider creates 'an order' in the EHR and a printout is initiated for the patient and the patient signs themselves up. Interviews with decision makers from our currently targeted sites will be used to explore the barriers and facilitators to the intervention implementation and adoption.

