13 SOURCE DOCUMENTS AND ACCESS TO SOURCE DATA/DOCUMENTS

Study staff will maintain appropriate medical and research records for this study, in compliance with ICH E6, Section 4.9 and regulatory and institutional requirements for the protection of confidentiality of subjects. Study staff will permit authorized representatives of NIDCR and regulatory agencies to examine (and when required by applicable law, to copy) research records for the purposes of quality assurance reviews, audits, and evaluation of the study safety, progress and data validity.

Access to source data and documents is controlled through strict physical and electronic controls. Staff access permissions will be set according to job description activities.

Source documents will include informed consent forms completed electronically in REDCap, a secure web-based application. Paper consent forms will be available as an alternative as necessary. This information will be kept in locked file cabinets, within a locked office within GSDM's research offices at [name] and only study staff will have keys. With the exception of the data collected through caregiver TMs, the remainder of the source documents will be eCRFs. These include iSMILE screener, iSMILE questionnaire, and caries assessment data capture systems, such as REDCAP. The iSMILE specific eCRFs were developed in concert with the CC as part of the qualitative and pilot phase. The eCRFs in CARIN were developed by UCSF's CC and successfully utilized by the Co-PIs during a previous RCT funded by the NIDCR (Oral Health Advocates in Public Housing).

Agile Health (AH) is our technology partner. The AH platform is the primary source of TM data. The platform, which is seen through a web-based user interface dashboard, requires permissions to access as well as a login. The dashboard allows our team to monitor incoming and outgoing messages in real-time, set personalization without help from a programmer, and respond to participant inactivity. The AH platform is HIPAA-compliant, with all PHI / PII data encrypted in transit and at rest, and messages are delivered through a secure gateway in an encrypted format.

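### Budget impact labour is priced at average salary, below the budget holder's actual outlay of salary plus employer on-costs

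*Combined protocol and SAP*

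**What the plan says.** Section 3.2.2 (Budget impact analysis) gives the only labour-costing rule in the plan. On quantity: "Labor time will be assessed for each dissemination scenario at each site". On price: "average salary for each personnel will be used to determine labor cost". A further sentence adds other items: "We will measure costs of interface development, implementation, and technical support". The section also makes a general commitment to a published budget-impact guideline. It does not mention fringe benefits, payroll taxes or any other loading on salary.

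Section 12.4 (Secondary aims, Aim 1) adopts the perspective of the budget holder who decides on uptake. It plans a cost for each case of caries prevented under each of two integration strategies. One is fully automated through the health record. The other is described in section 8.1 as "a more labor intensive strategy but less technologically complex approach". Technology costs come from surveys of IT specialists at the sites and of industry experts. Sensitivity analyses are planned, and decision makers will be able to change the assumptions.

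Elsewhere the plan describes staff work on messages. Section 5.4.2 leaves the Project Director and PIs unblinded because "they will need to monitor inbound text messages for any responses that the automated system does not recognize". Section 6.3 allows for the project director to reply to texts, and section 13 says: "The dashboard allows our team to monitor incoming and outgoing messages in real-time". The budget impact text in sections 3.2.2, 8.1 and 12.4 does not name this time as a cost item.

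**The concern.** The unit price does not match the declared perspective. A clinic that assigns staff time to a programme pays salary plus employer on-costs. Costing that time at salary alone gives a labour figure below what the budget holder pays.

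Secondary Aim 1 is meant to tell clinics what adopting and sustaining the oral health text programme would cost, and to compare two ways of doing it. Because the two strategies trade labour against technology, an error confined to the price of labour affects the comparison as well as the totals.

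**Working it through.** The plan gives no wage, hours, on-cost rate, technology cost or total, so there is no budget figure to reproduce. The size of the error can be written as algebra and illustrated over assumed ranges.

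**Notation.** T is non-labour cost, L is labour at salary, f is the employer on-cost rate as a fraction of salary, and s = L/(T+L) is the wage share of recorded cost. Subscript 1 is the automated strategy and subscript 2 the labour-intensive one. All values of f and s, and the example costs, are assumptions.

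**Step 1: the labour line.** Recorded labour is L and full labour is (1+f)L, so the understatement is 1 − 1/(1+f).
- f = 25%: 1 − 1/1.25 = 20.0%.
- f = 40%: 1 − 1/1.40 = 28.6%.

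**Step 2: total cost, with T fully priced.** The understatement as a fraction of full cost is sf/(1+sf).

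| Wage share s | f = 20% | f = 30% | f = 40% |
|---|---|---|---|
| 10% | 2.0% | 2.9% | 3.8% |
| 30% | 5.7% | 8.3% | 10.7% |
| 50% | 9.1% | 13.0% | 16.7% |
| 80% | 13.8% | 19.4% | 24.2% |

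For example, with s = 50% and f = 40%: 0.5 × 0.4 / (1 + 0.5 × 0.4) = 0.20/1.20 = 16.7%.

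**Step 3: the comparison of strategies.** Again with T fully priced, the recorded difference (strategy 2 minus strategy 1) is (T2+L2) − (T1+L1). The full difference exceeds it by f(L2−L1). That is the lean toward the labour-intensive strategy.

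The ranking changes only if the technology saving T1−T2 lies between L2−L1 and (1+f)(L2−L1). Take T1 = 100, L1 = 10, T2 = 60, L2 = 40 in arbitrary units. The technology saving is 40 and the extra labour is 30. As recorded, the totals are 110 and 100, so strategy 2 looks 10 cheaper.
- f = 20%: 112 against 108; strategy 2 is 4 cheaper.
- f = 30%: 113 against 112; strategy 2 is 1 cheaper.
- f = 40%: 114 against 116; strategy 2 is 2 dearer.

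The upper limit (1+f) × 30 is 36, 39 and 42 in turn. The saving of 40 falls inside the window only in the last case.

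**Step 4: message monitoring.** Add the same monitoring cost M to both strategies. The difference becomes (T2+(1+f)L2+M) − (T1+(1+f)L1+M), and M cancels. With M = 50 the three differences above are unchanged. Omitting M lowers both totals but does not move the comparison. If automatic enrolment brought in more users, so that M1 > M2, the omission would favour the automated strategy instead.

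**The case against.** The strongest reply is that the plan is silent on on-costs and does not exclude them. Salary might be loaded in practice, a guideline is cited, and users may alter the assumptions. Part of this stands: nobody can say from the documents what the analysts will do. But the specific sentence names average salary, and neither a general guideline reference nor an adjustable model replaces it. A base case that follows the sentence is low.

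Several stronger readings are tempting, and the documents do not support them.

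- *That the plan favours the labour-intensive strategy.* This needs technology to be priced more fully than labour. The plan does not say how site IT time will be priced. If that is also at salary, the lean shrinks or could reverse.
- *That the ranking of the strategies will change.* It changes only inside the window in step 3, and nothing in the plan shows that the costs fall there.
- *That monitoring and vendor charges are left out.* The site restriction belongs to the labour sentence. The implementation and technical support items in 3.2.2 could hold monitoring time, and the application costs surveyed under 12.4 could hold vendor charges.
- *That human monitoring helped to produce the trial effect and must therefore be costed.* Section 6.3 says that no human providers are used, and treats replies as a possible source of contamination to be checked. No section says that an adopting clinic would do or pay for this work.

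**Conclusion.** The point holds for the price of labour. Applied as written, the salary rule understates the budget holder's labour line by 20–29% for on-costs of 25–40%. For on-costs of 20–40%, total cost is understated by about 2–4% at a 10% wage share and about 9–17% at a 50% share. These sizes rest on assumed on-cost rates and wage shares, on salary meaning unloaded pay, and on non-labour costs being fully priced.

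The lean of f(L2−L1) toward the labour-intensive strategy is conditional in the same way, and a reversed ranking more so. The treatment of message monitoring and vendor charges is a matter for clarification. It is not a demonstrated omission, and it gives no reason to expect a bias toward the labour-intensive strategy. The point concerns a secondary aim and leaves the caries analysis untouched.

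**What to change.** 1. In section 3.2.2, replace average salary with average salary plus the employer's fringe and payroll-tax rate for each personnel type.
2. Apply the same basis to the time of site IT staff, so that labour and technology are priced alike in both strategies.
3. Add the on-cost rate to the parameters varied in the section 12.4 sensitivity analysis.
4. As a clarification, state whether inbound-text monitoring and reply time, and recurring vendor charges, fall under implementation and technical support or under application costs, or are excluded and why. If they are included, enter them equally per user in both strategies. The platform records message counts but not staff minutes, so monitoring time needs an assumed time per message with a range.

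The cost is a few sentences of plan text, an on-cost rate from each employer, and, if monitoring is included, a message count plus a stated time assumption. The reported cost of the oral health text programme would be slightly less favourable.

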4 STUDY DESIGN

This is a 2-arm, randomized controlled Phase III, single-center longitudinal trial. 850 parents or caregivers of children (< 7 years old) and their children with pediatric appointments at four targeted urban clinics will be recruited, consented, and subsequently randomized to OHT or CWT. We hypothesize that those randomized to the OHT group will have reduced incidence of caries as assessed by objective clinical exam 24- months after a baseline exam. Randomization will be a permuted block design, stratified by study site (Codman Square, Dorchester House, BMC, South End Community Health Center), and history of caries (no history of caries, any caries). Because of the sparsity of Spanish speaking participants, with Spanish speakers primarily concentrated at one site, we will not stratify by site language (English, Spanish) but only on caries history to yield 8 strata. CWT and OHT intervention arms will be matched on TM dose, duration and frequency, and employ identical features and engagement strategies for strong internal validity. External validity will be supported by the fact that participants will be proactively recruited from an existing channel (pediatric clinic appointments) and use of the text message program in their everyday lives. Recruitment sites are located in urban, low-income areas, and the population is ethnically diverse and on public assistance.

The approximate time to complete study enrollment is 1- year and the expected duration of subject participation is 2- years. A clinical exam to assess caries will take place at baseline and 12 and 24- months later. Clinical examiners are study staff and will be calibrated and blinded. Self-report surveys will take place at these time points, plus 2 and 4- months after baseline. These data will be captured through electronic data entry, in person, over the phone, or through an on-line link. Weekly and monthly assessments will also occur during the 4- month TM program (from baseline through 4-months post-baseline). The coordinating center (CC) will be University of California at San Francisco.

CWT or OHT TMs in either English or Spanish will be delivered in sets of two each day in Month 1, and one set per day in Months 2-4, exclusive of brief assessments by text. At month 12, participants will receive one month of 'booster' TMs (twice per day, exclusive of brief assessments by text). Features include: quizzes, customization, personalization, tailoring, interactivity, problem solving photos/video, goal setting, and feedback and rewards using a gamification approach. There will also be three 'weekly challenges' over the 4- month program in which both groups can 'opt-in' and earn weekly rewards and 'unlock' secret characters for performing the core targeted behavior (brushing and reading for OHT and CWT respectively). Target behaviors (Reading for CWT and Brushing for OHT) will be assessed daily via TMs during challenge weeks. Otherwise, both groups will be assessed weekly via TM on core topics (brushing for OHT; reading for CWT), motivation and confidence (to brush or to read). Monthly assessments include dental visits (OHT) or safety (CWT). Both groups will have the ability to choose 'choice topics' each week and will receive the same engagement strategies (quizzes, rewards, birthday texts).

CWT include the Core Topics Reading and Child Safety, and the Choice Topics Physical Activity, Healthy Development, Secondhand Smoke, Safety Hazards, Sleep and Behavior, and Stress tips for parents. CWT participants earn weekly badges for reading to their child. Participants who are not reading to their child at recommended levels will receive a graduated reward scheme, in which they will receive rewards for successive approximations of the recommended behavior. The goal is to engage with reading to their child every day. If they earn four different weekly badges (each badge specifying the reading goal achieved), they will earn a different 'Book Buddy' badge each month. They can also earn two 'mystery book buddies' for the completion of challenge weeks (Book buddies are anthropomorphized books).

OHT include the Core topics Brushing and Visiting the Dentist, and the Choice topics Bedtime routine, Bottle/Sippy cup use, Sugar Sweetened Beverages, Healthy Eating, Getting Fluoride and Fun Facts. OHT participants earn weekly badges for brushing (or supervising brushing) their child's teeth. Participants who are not brushing (or supervise brushing) their child's teeth at recommended levels will receive a graduated reward scheme, in which they will receive rewards for successive approximations of the recommended behavior. The goal is to brush their child's teeth (or supervise brushing) 6-7 days per week, twice per day. If they earn four different weekly badges (each badge specifying the brushing goal achieved), they will earn a different 'SuperTooth Hero' badge each month and collect an entire family of SuperTooth heroes (Charlie Chew, Molly Molar, Faye Fluoride and Captain Chomp). They can also earn two 'Secret Super Tooth Heroes' for the completion of challenge weeks. SuperTooth Heroes are anthropomorphized teeth wearing capes and holding toothbrushes.

Substudies

Because our comparison group (CWT) is an intervention, we would like to assess within- and between subject changes over time to gather pilot data for a future trial. The aim of this substudy would be to examine whether CWT parents increase their behaviors in two areas that reflect the core topics of the CWT intervention: reading to their child and child safety. Core topic text messages are given once per day during month one (choice topics are also given once per day in month one) and 4 days per week during months 2-4 (choice topics are given 3 days per week during months 2-4). Choice topics for CWT are: Physical Activity, Healthy Development, Secondhand Smoke, Safety Hazards, Sleep and Behavior, and Stress tips for parents. This substudy will have no impact on the main study. We will analyze data from all participants in CWT and examine within subject changes over time, as well as whether or not they differentially changed in key variables (reading, safety) vs. OHT. a separate analysis plan will be developed in the future.

5 STUDY ENROLLMENT AND WITHDRAWAL

5.1 Subject Inclusion Criteria

In order to be eligible to participate in this study, the caregiver and child must meet all of the following criteria, as applicable:

1. Provide informed consent for themselves and their child.
2. Willing to comply with all study procedures and be available for the duration of the study
3. Caregiver may be male or female, must be aged 18 or older (no upper age limit).

4. Caregiver must be a parent or legal guardian of a child less than 7 years old
5. Enrolled child must have their first tooth showing.
6. The child must receive medical care at one of the participating pediatric clinics (BMC, Dorchester House, Codman Square, South End Community Health Center).
7. Speak, understand, and read either English or Spanish fluently.
8. Have a mobile phone.
9. Have used any type of text messaging at least one time in the past month.
10. Have a mobile phone plan that includes unlimited text messaging.
11. Score above the literacy cut-off, i.e. score less than or equal to 3 on the Single Item Literacy Screener (Morris et al., 2006)
12. Ability to receive a test TM from the Agile Health system and 'opting-in' to program

5.2 Subject Exclusion Criteria

If the caregiver or child meets any of the following criteria, the dyad will be excluded from participation in this study:

1. Participated in our usability trial or RCT pilot trial
2. Substance abuse problems, as identified with the AUDIT-C screening tool and with questions about drug misuse.
3. Diagnosis of serious mental illness (Bipolar Disorder, Mania, Manic-depressive disorder, Schizophrenia, Psychosis), self-reported.
4. Children with severe congenital tooth malformations: at screening the caregiver will be asked if their child has known systemic diseases associated with abnormal tooth development or abnormal oral health status such as cleft lip or palate, amelogenesis imperfecta, or dentinogenesis imperfecta.
5. Currently enrolled in another mobile phone study.
6. Plan on moving out of the area during the next 2 years.

7. Plan on leaving the country for longer than two months during the 2- year study.
8. Enrolled in an oral health study or child health and wellness study.
9. Exclusion at the discretion of the Principal Investigator
10. Children who cannot complete the baseline oral health exam.

5.3 Strategies for Recruitment and Retention

The study target population includes parents or legal guardians (>18 years old) of children (< 7 years old) and their child with a pediatric appointment at one of the four participating clinical sites.

The primary recruitment method for the study will be RAs, or other trained study personnel, identifying and recruiting participants in participating clinic waiting rooms (and other clinic spaces deemed appropriate by clinic partners).

Additional strategies to identify potentially eligible participants may vary by site but include:

- (1) The site specific study champions and clinic staff and providers will identify potentially eligible participants, inform them about the study and direct them to a RA. If the RA isn't present, the clinic staff will give the participant a study pamphlet and/or permission to contact form for the iSmile study. The permission to contact form may be printed with pre-populated the patient's information (contact details), or given to the patient as a blank form.
- (2) iSMILE study staff will present the study at each clinical site at all-staff meetings to facilitate clinical staff and provider referral of potentially eligible participants to the iSMILE study;
- (3) Bilingual study advertising, with RA contact information, will be on display in study clinics;
- (4) Bilingual study advertising inviting interested clinic patients to attend study information session phone calls to learn more about the study;
- (5) "Warm-hand-off" phone calls will be conducted by the clinic-employed study champion to potentially eligible participants prior to their scheduled clinic appointment to confirm their upcoming appointment and determine interest in the study (no cold calls will be made by our research staff). If the person is interested, the person will be referred to our study staff;
- (6) Partnering with other studies happening at participating clinics to facilitate referrals to iSmile;
- (7) Sending an informational letter from the Pediatric Medical Director to potential participants.
- (8) Distributing recruitment materials (flyers, brochures and permission to contact forms) at Head Start locations because many parents who visit Head Start also bring their children to receive care at one of our recruitment sites.

Conducting "warm-hand-off" phone calls prior to a potentially eligible participants scheduled clinic visit will allow individuals the ability to plan for the extra time needed at their appointment to enroll and complete baseline study procedures. Research staff will identify subjects eligible for "warm-hand-off" phone calls from participating clinics' appointment schedule (part of the electronic health record (EHR). Research staff will have 'read-only' access to the EHR and they will not have access to the medical portion of the record. The parts of the EHR that we will have access to contains information on upcoming clinic appointments (date/time), name of parent and child, contact information, and age of child. The "warm-hand-off" phone call between clinic personnel and RAs will involve a phone call from clinic personnel to a potentially eligible subject

to confirm their upcoming appointment and then determine their interest in learning more about the iSmile study. If the potentially eligible subject wants to learn more about the iSmile study over the phone, the clinical staff will hand the phone off to the iSmile RA.

The iSmile study team will partner with other studies happening at participating clinics to facilitate referrals to iSmile. The iSmile team has learned of the other co-occurring studies happening in each of the participating clinics that overlap with the target iSmile recruitment population. From these co-occurring studies, iSmile has worked with each applicable study contact to determine if cross recruitment is feasible. For those studies for which cross recruitment is feasible, co-occurring study staff members will screen their potential participants per their IRB approved protocol. For potential participants who screen ineligible for other co-occurring studies, the co-occurring study staff conducting screening will inform the individual that they may be eligible for the iSmile study. If an iSmile study staff member is available, the potential participant will be directly introduced to the iSmile study staff member to hear more about the study and potentially complete the IRB approved screening and enrollment process. If an iSmile study staff member is not available to tell the potential participant more about the study, the co-occurring study staff member will inform the potential participant that they can complete a paper permission to contact form and a member of the iSmile study staff will contact them shortly to tell them more about the study. Each participating clinical site has designated its own secure location for completed permission to contact forms to be stored on site until an iSmile study staff member is able to collect them. After collection, iSmile study staff will attempt to contact all potential participants to tell them more about the study. After successfully, or unsuccessfully, attempting to contact the potential participant, all completed permission to contact forms will be stored in a locked filing cabinet in the Research Project Manager's office.

The informational letter being sent from each pediatric clinic, from the Pediatric Medical Director, will inform parents of children under age 7 that the health center is partnering with Boston University to develop a text message program. Study staff contact information is also included in the letter, should the parent be interested in assessing eligibility or asking questions about the study.

If participants do not have time to be screened at the clinic, we will collect their contact information and the participant will be screened over the phone. Participants who are called will be guided through the consent process over the phone and we will obtain verbal consent over the phone (seeking a waiver of documentation of consent) until they can provide signed consent at the time of the clinical exam. This is so participants can spend less time doing study procedures at the clinic. Clinic staff will also refer potentially interested participants to RAs.

Study staff will perform screening and informed consent (in a private space or on the phone, prior to their appointment). Participants will be told that, in order to be eligible for the study, they must be willing to receive TMs about their child's health, have a phone that is able to send/receive text messages from our system, give permission for the index child to have dental exam, opt-in to the program, and receive one of two different TM programs. If there is more than one child < 7 years old in the same family, we will systematically choose the youngest as the index child for the study. If there is more than one parent present, we will choose the one that spends the most time with the child. Those who are eligible to participate will be asked to sign an electronic informed consent form, complete contact information and child demographic information with study staff who will verbally collect information via direct entry, and subsequently complete a self-report baseline assessment via electronic data capture (with

paper copies as back-up) and the baseline oral assessment. Study staff will take all possible steps to ensure that the participant is clear that the baseline questionnaire will ask questions regarding themselves and the child in the study (youngest child under the age of 7 years old with at least one tooth showing i.e., child for whom the informed consent had been collected). Once the baseline questionnaire and oral assessment are completed, REDCAP will automatically randomize participants into OHT or CWT, and this code as well as the TM personalization options will be transferred to the AH system so the first TM (OHT or CWT) will occur within 24 hours after randomization. The automation of randomization will ensure that the RAs are blind to treatment condition.

The enrolled parent/caregiver will receive \$60 for assessment contacts that include a self-report instrument and an oral health assessment conducted by the study clinical examiner (baseline and 12 and 24- months), \$40 for assessment contacts which only include the self-report instrument (2 and 4- months after baseline), an additional \$40.00 if the 12 and 24 month plus either the 2 or 4 month assessments are completed, or \$70.00 if all 4 assessments are completed. Thus, the total possible compensation for each parent who is a participant is \$330.00. If at any point during the study following baseline it is determined that a participant will not be able to complete the 12 or 24 month oral health exam because they moved out of the area, we would still like to compensate the participant for completing the 12 or 24 month follow up surveys without the oral health exam. The participant would then be compensated with a \$40 gift card instead of \$60, which is comparable to compensation at 2 and 4 months when participants are expected to only complete surveys. In addition, individuals who move out of the area and their situation is deemed by study research staff to be impossible to complete the oral health assessment are still eligible for bonus payment.

During the text message program, participants will be given brief weekly assessments. Each time they provide an answer to these questions, their name will be entered into a monthly raffle for \$100.00. Every time that they answer one of these questions, they will have another entry into the raffle, increasing their chances of winning each month, for a maximum of four chances. Therefore, if they answer each of the four weekly questions per month, they will have four entries into the raffle that month. After the name is drawn for that month, a new month will begin and all previous entries will be cleared. Because they will receive text messages over the course of four months, they will have four chances to win.

Assessments will be completed online, on participant's smartphone, on the phone, or in person.

To prevent dropout during the 4- month intervention period, we will personalize TMs, avoid TM redundancy, vary TM content and frequency, use participant's name and use fun TM quizzes, with the answers provided the following day. After the intervention period, we will use various cohort maintenance procedures as outlined in Albino et al (2017) to enhance retention (e.g., send birthday cards, contact six times/year to find out address changes) and also track participants through their contact with the pediatric clinics (i.e. identification of upcoming child wellness appointments through the clinic's electronic scheduling system. Guidance from the AB will also assist in the development of retention strategies.

In addition to direct compensation for their participation in the study, participants will also have be compensated for their transportation to and from participating clinical sites. As the Baseline

enrollment process is long, not all families who begin the enrollment process are able to complete it in one day. To help facilitate enrollment, the study will compensate participants in the form of a \$10 gift card for their transportation to and from participating clinical sites for participants who need to return to complete their enrollment process in a second visit. In addition, the study will provide the same \$10 gift card compensation for participant transportation to and from participating clinical sites for enrollees to complete the 12 and 24 month oral health assessments at the clinic site.

